### **9.4. Vital Signs**

Descriptive summaries of observed values and changes from baseline will be calculated for systolic blood pressure, diastolic blood pressure, heart rate, height, weight, body mass index and oral body temperature by treatment group and visit.

Changes in weight by treatment group will summarize the number of subjects who gain or lose  $\geq 5\%$  of their baseline body weight during the course of the study, as well as subjects who gain or lose  $\geq 10\%$  of their baseline body weight over the course of the study by treatment group and visit.

BMI is derived as specified in [Section 6.1.7](#). Shift tables (overall, subjects who indicated weight loss was intentional and subjects weight loss was not intentional at each visit) by treatment group for subjects who shift from their baseline BMI category (underweight, normal, overweight, obese) to a different BMI category throughout the course of the study will be provided by treatment group and visit.

### **9.5. PHQ-8 and Modified PHQ-A**

PHQ-8 will be completed by adult subjects and modified PHQ-8 is filled by adolescent subjects of age 12-17 years inclusive. Data for PHQ-8 and Modified PHQ-A will be classified using each subject's total score at a time point into a category based on the following scoring system:

- None – Minimal depression (0 to 4)
- Mild depression (5 to 9)
- Moderate depression (10 to 14)
- Moderately severe depression (15 to 19)
- Severe depression (20 to 24)

Shift tables showing the category of severity at each time point by treatment group will be presented.

## **9.6. CDI-2**

Parents/caregivers will complete the CDI-2 for subjects belonging to 9-11 years of age inclusive. For Children’s Depression Inventory 2(CDI-2), descriptive summaries of observed values and changes from baseline will be calculated for the total score and the 2 scales emotional problems and functional problems by treatment group and visit.

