#### **4.8.6. Removal of Subjects from Investigational Product**

A subject may discontinue from receiving the IP for any of the following reasons:

- Occurrence of any medical condition or circumstance that, in the opinion of the Investigator, exposes the subject to substantial risk and/or does not allow the subject to adhere to the requirements for IP administration as per the Protocol.
- Occurrence of or considerable worsening of an AE (described in [Section 5.7](#)) that, in the opinion of the Investigator in consultation with the Medical Monitor and Sponsor, represents an unacceptable risk to the subject if he/she continues in the study. The Investigator must follow the subject until the AE resolves or satisfactorily stabilizes.
- IP application must be discontinued immediately in the event of a female subject's pregnancy.
- Subject's decision to withdraw from receiving IP.
- Weight loss of >5% from Baseline, if not dieting or intentionally trying to lose weight, at the Investigator's discretion and after consultation with the Medical Monitor and Sponsor.
- C-SSRS indicative of suicidal ideation
- PHQ-8/PHQ-A score  $\geq 15$  if determined by Investigator in consultation with a mental health professional.
- CDI-2 raw score of  $\geq 32$  if determined by Investigator in consultation with a mental health professional.
- Requirement for use of prohibited concomitant medication ([Table 1](#)) after consultation with the Sponsor and Medical Monitor.
- Subjects repeated failure to comply with protocol requirements or study related procedures.

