### **5.1.9. Children's Depression Inventory 2 (Parent Report)**

The CDI-2 Assessment will be performed according to the Schedule of Assessments ([Section 1.3](#)) for subjects 9-11 years old, inclusive. Subjects 9-11 years old at the time of assent will complete the CDI-2 throughout the study.

The CDI-2 quantifies depressive symptomatology using reports from children/adolescents, teachers, and parents or caregivers. It is recommended for use in initial evaluation and is appropriate when there is a need for an assessment and robust description of a child's depressive symptoms.

This study will use the CDI Parent Report Form. An example of the Parent Report Form is presented in [Appendix 4](#).

A subject with a CDI-2 raw total score of  $\geq 21$  for females and  $\geq 22$  for males should be referred to a mental health professional for evaluation.

A subject with a CDI-2 raw total score of  $\geq 32$  should be referred to a mental health professional, and Investigators in consultation with the mental health professional should consider interruption or discontinuation of the investigational product.

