## **4. STATISTICAL ANALYSIS AND REPORTING**

### **4.1. Introduction**

Data processing, tabulation of descriptive statistics, calculation of inferential statistics, and graphical representations primarily use SAS (release 9.4 or higher). If the use of other software is warranted, the final statistical methodology report will detail what software was used for what purposes.

Continuous (quantitative) variable summaries will include the number of subjects (n) with non-missing values, mean, standard deviation (SD), median, Q1, Q3, minimum, and maximum.

Categorical (qualitative) variable summaries will include the frequency and percentage of subjects who are in the particular category or each possible value. In general, the denominator for the percentage calculation will be based upon the total number of subjects in the study population for each treatment group unless otherwise specified.

The minimum and maximum will be reported with the same degree of precision (ie, the same number of decimal places) as the observed data. Measures of location (mean and median) will be reported to 1 degree of precision more than the observed data and measures of spread (SD) will be reported to 2 degrees of precision more than the observed data.

Percentages will be presented to 1 decimal place, unless otherwise specified.

Unless otherwise indicated in section 6.1.3, all statistical tests will be conducted at the 0.01 significance level using 2-tailed tests, and p-values will be reported. Corresponding 95% and 99% confidence intervals (CIs) will be presented for statistical tests.

ARQ-154 0.3% foam will be described as “Roflumilast foam 0.3%” throughout the tables, figures, and listings.

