14.3.3.1	Safety	Summary of Clinical Chemistry Laboratory Results (Standard Units) by Study Visit
14.3.3.2	Safety	Shift from Baseline in Clinical Chemistry Laboratory Results (Standard Units) by Study Visit
14.3.3.3	Safety	Summary of Hematology Laboratory Results (Standard Units) by Study Visit
14.3.3.4	Safety	Shift from Baseline in Hematology Laboratory Results (Standard Units) by Study Visit
14.3.3.5	Safety	Summary of Quantitative Urinalysis Laboratory Results (Standard Units) by Study Visit
14.3.3.6	Safety	Shift from Baseline in Quantitative Urinalysis Laboratory Results (Standard Units) by Study Visit
14.3.3.7	Safety	Summary of Qualitative Urinalysis Laboratory Results (Standard Units) by Study Visit
14.3.4.1	Safety	Summary of Vital Signs by Study Visit
14.3.4.2	Safety	Change in Weight from Baseline by Study Visit
14.3.4.3	Safety	Shift from Baseline in BMI by Study Visit
14.3.4.4	Safety	Change in Weight from Baseline by Study Visit – by Weight Loss Intentional/Non-Intentional
14.3.4.5	Safety	Shift from Baseline in BMI by Study Visit - by Weight Loss Intentional/Non-Intentional
14.3.5	Safety	Shift from Baseline in Patient Health Questionnaire (PHQ-8)/Modified PHQ-Adolescents by Study Visit
14.3.6	Safety	Summary of CDI-2 by Study Visit
14.3.7	Safety	Summary of Columbia-Suicide Severity Rating Scale (C-SSRS) Suicidal Ideation and Suicidal Behavior by Study Visit
14.3.8	Safety	Summary of Physical Examination by Study Visit
14.3.9	Safety	Summary of Concomitant Medications by Anatomic Therapeutic Chemical (ATC) Class Level 4 and Preferred Term
14.3.10	Safety	Summary of Pigmentation Assessment by Race
14.3.10.1	Safety	Shift from Baseline in Hypopigmentation by Study Visit
14.3.10.2	Safety	Shift from Baseline in Hyperpigmentation by Study Visit
14.4	Pharmacokinetic Data	
14.4.1	PK	Summary of Pharmacokinetic Concentration Results by Study Visit

\*Analyses of Scalpdex will be limited to subjects in the ITT population who have Seborrheic Dermatitis involvement on the scalp

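### No planned output counts the children aged 9-11 who reach the protocol's own CDI-2 action thresholds; the score is summarised only as a continuous variable

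*SAP*

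**What the plan says.** **Thresholds.** Protocol 5.1.9 calls for referral at a "CDI-2 raw total score of $\geq 21$ for females and $\geq 22$ for males". At 32 or more the child is referred and investigators, with the mental health professional, "should consider interruption or discontinuation of the investigational product". Protocol 5.9 repeats both levels. Protocol 4.8.6 lists a score of 32 or more among the reasons for removal from treatment, "if determined by Investigator in consultation with a mental health professional". Exclusion 5 keeps out children scoring 17 or more (girls) or 18 or more (boys) at Screening or Baseline.

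**Who is covered.** Footnote k to the Protocol 1.3 schedule starts the C-SSRS at age 12, gives PHQ-A to ages 12-17 and PHQ-8 to adults. Children aged 9-11 have CDI-2 alone, at Screening, Baseline, Week 4 and Week 8.

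**Planned analysis.** SAP 9.6 states that "descriptive summaries of observed values and changes from baseline will be calculated for the total score and the 2 scales", by arm and visit. SAP 4.1 defines a continuous summary as the number of non-missing values plus "mean, standard deviation (SD), median, Q1, Q3, minimum, and maximum". The only CDI-2 output in SAP 14.1 is Table 14.3.6, "Summary of CDI-2 by Study Visit".

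**Other safety measures.** For PHQ-8 and PHQ-A, SAP 9.5 says: "Shift tables showing the category of severity at each time point by treatment group will be presented". SAP 9.7 gives frequencies of C-SSRS positive answers. SAP 9.4 counts subjects who gain or lose at least 5% and at least 10% of body weight.

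**Listings.** SAP 6.1.8 says that everything collected will be listed. The index in SAP 14.3 names no CDI-2 listing.

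**The concern.** The thresholds exist to pick out an individual child whose score has risen far enough to need action. The matching safety question is how many children in each arm reached that point, and no planned table answers it. The youngest subjects are the only ones whose depression measure is reported without categories or counts, and they have no C-SSRS alongside it.

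A count would be easy to interpret here. Because of exclusion 5, and apart from eligibility deviations, any post-baseline total at or above 21/22 is a new crossing on study.

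Protocol 2.4.2 gives psychiatric adverse events among the effects to be monitored. Those are described for oral roflumilast in COPD patients, so the text supports monitoring; it does not establish a harm of the foam.

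**Working it through.** **1. The plan's own figure.** SAP 6.1.7 gives a CDI-2 total of 0 to 51. It has 17 items scored 0-3: 17 × 3 = 51. The scales have 9 and 8 items, and 9 + 8 = 17. The figure reproduces.

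**2. Room between entry and action.** Scores are whole numbers, so the highest eligible baseline is 16 (girls) or 17 (boys). The smallest rise that reaches referral is 21 − 16 = 5 or 22 − 17 = 5. The smallest that reaches 32 is 32 − 16 = 16 or 32 − 17 = 15. A change score alone does not identify a crossing: a rise of 5 crosses from the highest eligible baseline but not from 10.

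**3. What the mean and median show.** The number of children aged 9-11 is not given, so n per arm is an assumption. Let every child start at 10, one child rise and the rest stay put. The mean change is rise/n.

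| n in arm | one child to 22 (+12) | one child to 32 (+22) | median | maximum |
|---|---|---|---|---|
| 4 | 3.0 | 5.5 | 10 | 22 or 32 |
| 10 | 1.2 | 2.2 | 10 | 22 or 32 |
| 20 | 0.6 | 1.1 | 10 | 22 or 32 |

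If each other child instead falls by 2, the mean change is (22 − 2(n − 1))/n: +2.8 for n = 5, +0.4 for n = 10 and −0.8 for n = 20. The mean can point towards improvement, but the maximum would still print 32 and the maximum change +22.

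**4. What the maximum does not show.**

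- *How many children.* Take n = 10. Set A is 23, 22, 22 and seven 5s; set B is 23, eight 9s and one 7. The sums are 23 + 44 + 35 = 102 and 23 + 72 + 7 = 102. Both have mean 10.2 and maximum 23, but three children in A and one in B are at 22 or more. These sets do differ in median (5 against 9) and upper quartile, so a careful reader could separate them. That help fails when few children cross. With n = 20 the upper quartile lies between the 15th and 16th ordered values, so one to four crossings all sit above it.
- *Which sex.* 22 or more is a referral score for either sex, and 20 or less for neither. A 21 is a referral score for a girl but not for a boy, and nothing in SAP 9.6 or the title of Table 14.3.6 indicates a split by sex.
- *Same child or not.* High maxima at both Week 4 and Week 8 could be one child twice or two children.

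**5. Other outputs.** Adverse event and discontinuation tables would show a crossing only if it was recorded as an adverse event or led to stopping. Neither document requires a crossing to be recorded as an event, and stopping at 32 is a matter of judgement. The listing promised in SAP 6.1.8 would settle all three ambiguities, but the index does not contain it.

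**The case against.** A reader might infer that CDI-2 is reported by means alone, so that a child's deterioration could disappear into the group average. The documents do not support that. SAP 4.1 makes the minimum and maximum part of every continuous summary, and SAP 9.6 applies such summaries to both scores and changes. A child who reached 32 would be visible as the maximum of an arm and visit.

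A reader might also infer that such a child would go unnoticed in the trial. The protocol acts on each child's own score at the visit, so any deficit is in aggregate reporting.

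Three further points have force:

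- SAP 6.1.8 does promise listings of all collected data. The index also omits PHQ-8/PHQ-A, C-SSRS, pigmentation and tolerability, so the mismatch is general and not peculiar to CDI-2. The table shells are in a separate document, and the layout of Table 14.3.6 is unknown.
- The protocol defines five severity categories for PHQ-8 and PHQ-A but none for CDI-2, only entry and action cut-offs. Treating the instruments differently is not a contradiction.
- The group may be very small, and any table added now is post hoc.

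These points limit the concern but do not answer it. A maximum is not a count, the sex-specific threshold cannot be read from a pooled summary, and a general promise of listings that its own index omits is not a planned output.

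**Conclusion.** The point holds as a reporting gap of moderate weight. CDI-2 is summarised only as a continuous score, and no planned table gives the number of children at or above 21 (girls)/22 (boys) or 32. The planned summary would reveal that someone reached 32; it would not give the number of children crossing either threshold, or settle a score of 21.

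The absence of a count follows directly from SAP 9.6 and 14.1. The numerical examples rest on assumed group sizes (4 to 20 per arm) and assumed scores, because the documents do not state how many children aged 9-11 were enrolled. If there were very few, the full summary might allow the count to be worked out, and a listing would matter more than a table. No efficacy conclusion is affected, and nothing here questions the thresholds or the management attached to them.

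**What to change.** 1. In SAP 9.6 and Table 14.3.6, add n (%) of children by arm, at each post-baseline visit and for the highest post-baseline total, (a) at or above 21 for girls and 22 for boys and (b) at or above 32. Apply the cut-offs by sex. Use as denominator the children with a CDI-2 total at that visit, or with at least one post-baseline total. Keep the continuous summaries.
2. Add a by-subject CDI-2 listing to SAP 14.3 with arm, sex, visit, total and both scale scores. This brings the index into line with SAP 6.1.8 for this instrument; the other unlisted instruments should be reconciled at the same time.
3. A full baseline shift table is not needed: exclusion 5 leaves essentially one baseline row.

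The cost is a few lines of SAP text, one table extension and one listing, all from data already collected. SAP 9 plans no inferential safety tests, so there is no alpha cost. There are two downsides. Counts will be small and should be shown as n with the denominator. The database was locked on 17 May 2022 and unblinded on 19 May 2022, before SAP V3.0 of 22 September 2022, so the output must be labelled in the study report as added after lock and unblinding, as SAP 10.1 requires.

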## **9.7. C-SSRS**

The C-SSRS is a questionnaire that prospectively assesses Suicidal Ideation and Suicidal Behavior. At the Screening study visit, “Baseline/Screening” version of the C-SSRS will be used. This version assesses Suicidal Ideation and Suicidal Behavior during the subject’s lifetime and during the past 6 months. For the Screening visit, “lifetime” experience of the subject with Suicidal Ideation and Suicidal Behavior will be summarized. From Baseline visit, the “Since Last Visit” version will be used.

Tables will include results from the Suicidal Ideation and Suicidal Behavior sections of the C-SSRS. Frequencies and percentages of subjects with a response of “Yes” at any point on the Suicidal Ideation and Suicidal Behavior items will be summarized by study visit and treatment group.

## **9.8. Physical Examination**

The number and percentage of subjects with normal and abnormal findings in the physical examination will be displayed at each study visit and treatment group.

## **9.9. Concomitant Medication**

Prior and concomitant medications will be summarized descriptively by treatment group, ATC level 4, and preferred term using counts and percentages.

Prior medications will be presented separately from concomitant medications. Medications that started before the first application of IP will be considered prior medications whether or not they were stopped prior to the first application of study drug. Any medications continuing or starting after the first application of study drug will be considered to be concomitant. If a medication starts before the first application of study drug and continues after the first application of study drug it will be considered both prior and concomitant.

Medications will be coded using WHODrug Global B3, version September 2021.

## **9.10. Pigmentation Assessment**

Hypopigmentation and hyperpigmentation are scored individually on a 0-3 scale where '0' indicates none, '1' for mild, '2' for moderate and '3' for severe. A shift table of hypopigmentation at baseline and at each study visit will be provided by treatment group as well as the shift table of hyperpigmentation. Proportion of subjects who achieves no hypopigmentation and hyperpigmentation at each study visit will be summarized for those subjects who presents of Hypopigmentation or/and hyperpigmentation at baseline. Categorical summary of pigmentation assessment will be provided by study visit and treatment group stratified by race groups (white, others, overall).

# **10. CHANGES FROM PLANNED ANALYSIS**

## **10.1. Version 2.0**

Version 2.0 of the SAP is based on the final signed version of Amendment 2 for the ARQ-154-304 protocol. At the time of signing this SAP version 2.0, the protocol is in the process of being published and is planned to undergo IRB review and approval after database lock.

The intent of this SAP is to document, prior to study database lock and unblinding, the changes specified in protocol amendment 2 regarding the testing strategy used for the secondary endpoints and also other minor updates to analyses not detailed in the protocol. Any changes to the final protocol or additional analyses created after database lock and unblinding will be clearly labeled as such in the CSR.

## **10.2. Version 3.0**

Section 1 Overview provides a description of the rationale for SAP Version 3. The purpose of the SAP is to document the change to the primary estimand and related multiple imputation strategies. The revised estimand will be the focus of the Clinical Study Report and NDA. Key results based on the original estimand defined in SAP versions 1 and 2 will be provided as supplemental information for the primary and secondary endpoints covered by the multiple

testing strategy.

## **11. OTHER PLANNED ANALYSIS**

### **11.1. Pharmacokinetic Analysis**

Concentration data will be summarized by timepoint and treatment group using descriptive statistics, reporting n, mean, standard deviation, median, Q1, Q3, minimum, and maximum, and geometric statistics including geometric mean and coefficient of variation. For computation of mean plasma concentrations, data that are below the limit of quantification (BLQ) will be set to zero. The PK population will be used for these analyses.

All PK collection information from the eCRF will be presented in a listing. PK concentration results will be listed as well.

## **12. CHANGES TO ANALYSIS PLANNED IN THE PROTOCOL**

### **12.1. Definition of PK Population**

In this SAP, PK population is defined as subjects who received at least one confirmed dose of investigational product (IP) and provided at least one PK sample. This population will be used for summary of PK concentration results. The definition is different from that in protocol where PK population is defined as subjects receiving active drug with sufficient plasma concentrations of roflumilast to define a profile, as determined by the pharmacokineticist, which will be used for analysis of PK parameters.

## 14. TABLES, LISTINGS AND FIGURES

All listings, tables, and graphs will have a header showing the sponsor company name and protocol and a footer showing the version of SAS, the file name and path, and the source of the data (listing number).

### 14.1. Planned Table Descriptions

The following are planned summary tables for protocol number ARQ-154-304. The table numbers are place holders only and may be changed when the tables are produced.

Table Number	Population	Table Title/Summary
14.1		Disposition, Baseline Characteristics and Exposure Summary
14.1.1	All Subjects	Subject Disposition
14.1.2.1	ITT	Demographics and Baseline Characteristics
14.1.2.2	Safety	Demographics and Baseline Characteristics
14.1.3	Safety	Previous Treatment History for Seborrheic Dermatitis
14.1.4	ITT	Protocol Deviations
14.1.5	Safety	Prior Medications by Anatomic Therapeutic Chemical (ATC) Class Level 4 and Preferred Term
14.1.6	Safety	Exposure to Investigational Product
14.2		Efficacy Summary
14.2.1	ITT	Hypothesis Testing for Primary and Secondary Efficacy Endpoints – Multiple Imputation
14.2.1.1	ITT	Investigator Global Assessment (IGA) Grades and Success by Study Visit – Multiple Imputation (Primary Analysis) Categorical Results
14.2.1.1.s	ITT	Investigator Global Assessment (IGA) Grades and Success by Study Visit – Multiple Imputation (Primary Analysis, Supplemental Estimand) Categorical Results
14.2.1.2.1	PP	Investigator Global Assessment (IGA) Grades and Success by Study Visit – Observed Data (Supplemental Analysis) Categorical Results
14.2.1.2.2	mITT	Investigator Global Assessment (IGA) Grades and Success by Study Visit – Multiple Imputation (Sensitivity Analysis) Categorical Results
14.2.1.2.3	ITT	Investigator Global Assessment (IGA) Grades and Success by Study Visit – Observed Data (Sensitivity Analysis) Categorical Results
14.2.1.2.4	ITT	Investigator Global Assessment (IGA) Grades and Success by Study Visit – Non-responder Imputation (Sensitivity Analysis) Categorical Results
14.2.1.2.5	ITT	Investigator Global Assessment (IGA) Grades and Success at Week 8 – Tipping Point Analysis (Sensitivity Analysis)
14.2.1.2.6.1	ITT	Investigator Global Assessment (IGA) Success at Week 8 by Site – Observed data (Supporting Analysis)

Table Number	Population	Table Title/Summary
14.2.1.2.6.2	ITT	Investigator Global Assessment (IGA) Success at Week 8 – Multiple Imputation, Impact of Site (Supporting Analysis)
14.2.1.2.7	ITT	Investigator Global Assessment (IGA) Grades and Success at Week 8 – Multiple Imputation, without Site Stratification (Sensitivity Analysis) Categorical Results
14.2.1.3.1	ITT	Investigator Global Assessment (IGA) Grades and Success by Study Visit and Response to Topical Corticosteroids – Multiple Imputation (Subgroup Analysis)
14.2.1.3.2	ITT	Investigator Global Assessment (IGA) Grades and Success by Study Visit and Response to Topical Antifungals – Multiple Imputation (Subgroup Analysis)
14.2.1.3.3	ITT	Investigator Global Assessment (IGA) Grades and Success by Study Visit by Study Visit and Age Group – Multiple Imputation (Subgroup Analysis)
14.2.1.3.4	ITT	Investigator Global Assessment (IGA) Grades and Success by Study Visit by Study Visit and Baseline IGA Disease Severity – Multiple Imputation (Subgroup Analysis)
14.2.1.3.5	ITT	Investigator Global Assessment (IGA) Grades and Success by Study Visit and Gender – Multiple Imputation (Subgroup Analysis)
14.2.1.3.6	ITT	Investigator Global Assessment (IGA) Grades and Success by Study Visit and Ethnicity – Multiple Imputation (Subgroup Analysis)
14.2.1.3.7	ITT	Investigator Global Assessment (IGA) Grades and Success by Study Visit and Race – Multiple Imputation (Subgroup Analysis)
14.2.1.3.8	ITT	Investigator Global Assessment (IGA) Grades and Success by Study Visit and Baseline BSA% – Multiple Imputation (Subgroup Analysis)
14.2.1.3.9	ITT	Investigator Global Assessment (IGA) Grades and Success by Study Visit and Baseline BSA% Tertiles – Multiple Imputation (Subgroup Analysis)
14.2.1.3.10	ITT	Investigator Global Assessment (IGA) Grades and Success by Study Visit and Fitzpatrick Score – Multiple Imputation (Subgroup Analysis)
14.2.1.3.11	ITT	Investigator Global Assessment (IGA) Grades and Success by Study Visit and Body Part Involvement – Multiple Imputation (Subgroup Analysis)
14.2.1.4	ITT	Summary of Investigator Global Assessment (IGA) by Study Visit – Observed Data
14.2.2.1	PRU4-ITT	Worst Itch-Numeric Rating Scale (WI-NRS) Success by Study Visit – Multiple Imputation (Primary Analysis)
14.2.2.1.s	PRU4-ITT	Worst Itch-Numeric Rating Scale (WI-NRS) Success by Study Visit – Multiple Imputation (Primary Analysis, Supplemental Estimand)
14.2.2.2.1	PRU4-ITT	Worst Itch-Numeric Rating Scale (WI-NRS) Success by Study Visit – Observed Data (Sensitivity Analysis)

Table Number	Population	Table Title/Summary
14.2.2.2.2	PRU4-ITT	Worst Itch-Numeric Rating Scale (WI-NRS) Success by Study Visit - Non-responder Imputation (Sensitivity Analysis)
14.2.2.3.1	PRU4-ITT	Worst Itch-Numeric Rating Scale (WI-NRS) Success by Study Visit and Response to Topical Corticosteroids - Multiple Imputation (Subgroup Analysis)
14.2.2.3.2	PRU4-ITT	Worst Itch-Numeric Rating Scale (WI-NRS) Success by Study Visit and Response to Topical Antifungals - Multiple Imputation (Subgroup Analysis)
14.2.2.3.3	PRU4-ITT	Worst Itch-Numeric Rating Scale (WI-NRS) Success by Study Visit and Age Group - Multiple Imputation (Subgroup Analysis)
14.2.2.3.4	PRU4-ITT	Worst Itch-Numeric Rating Scale (WI-NRS) Success by Study Visit and Baseline IGA Disease Severity - Multiple Imputation (Subgroup Analysis)
14.2.2.3.5	PRU4-ITT	Worst Itch-Numeric Rating Scale (WI-NRS) Success by Study Visit and Gender - Multiple Imputation (Subgroup Analysis)
14.2.2.3.6	PRU4-ITT	Worst Itch-Numeric Rating Scale (WI-NRS) Success by Study Visit and Ethnicity - Multiple Imputation (Subgroup Analysis)
14.2.2.3.7	PRU4-ITT	Worst Itch-Numeric Rating Scale (WI-NRS) by Study Visit and Race - Multiple Imputation (Subgroup Analysis)
14.2.2.3.8	PRU4-ITT	Worst Itch-Numeric Rating Scale (WI-NRS) Success by Study Visit and Baseline BSA% - Multiple Imputation (Subgroup Analysis)
14.2.2.3.9	PRU4-ITT	Worst Itch-Numeric Rating Scale (WI-NRS) Success by Study Visit and Baseline BSA% Tertiles - Multiple Imputation (Subgroup Analysis)
14.2.2.3.10	PRU4-ITT	Worst Itch-Numeric Rating Scale (WI-NRS) Success by Study Visit and Fitzpatrick Score - Multiple Imputation (Subgroup Analysis)
14.2.2.3.11	PRU4-ITT	Worst Itch-Numeric Rating Scale (WI-NRS) Success by Study Visit and Body Part Involvement - Multiple Imputation (Subgroup Analysis)
14.2.2.4	ITT	Achievement of Daily Worst Itch-Numeric Rating Scale (WI-NRS) 0 or 1 by Study Visit - Observed Data
14.2.2.5	ITT	Summary of Average Weekly Worst Itch-Numeric Rating Scale (WI-NRS) by Study Visit - Observed Data
14.2.2.6	ITT	Change from Baseline in Average Weekly Worst Itch-Numeric Rating Scale (WI-NRS) by Study Week - Observed Data (ANCOVA)
14.2.2.7	ITT	Worst Itch-Numeric Rating Score (WI-NRS) by Study Visit Categorical Results
14.2.2.8	ITT	Change from Baseline in Daily Worst Itch-Numeric Rating Scale (WI-NRS) by Study Week - Observed Data (ANCOVA)
14.2.3.1	ITT	Overall Assessment of Erythema Severity Grades by Study Visit - Multiple Imputation (Primary Analysis) Categorical Results

Table Number	Population	Table Title/Summary
14.2.3.1.s	ITT	Overall Assessment of Erythema Severity Grades by Study Visit - Multiple Imputation (Primary Analysis, Supplemental Estimand) Categorical Results
14.2.3.2.1	ITT	Overall Assessment of Erythema Severity Grades by Study Visit – Observed Data (Sensitivity Analysis) Categorical Results
14.2.3.2.2	ITT	Overall Assessment of Erythema Score of 0 at Week 8 - Non-responder Imputation – (Sensitivity Analysis)
14.2.3.3.1	ITT	Overall Assessment of Erythema Score of 0 at Week 8 by Response to Topical Corticosteroids - Multiple Imputation (Subgroup Analysis)
14.2.3.3.2	ITT	Overall Assessment of Erythema Score of 0 at Week 8 by Response to Topical Antifungals - Multiple Imputation (Subgroup Analysis)
14.2.3.3.3	ITT	Overall Assessment of Erythema Score of 0 at Week 8 by Age Group - Multiple Imputation (Subgroup Analysis)
14.2.3.3.4	ITT	Overall Assessment of Erythema Score of 0 at Week 8 by Baseline IGA Severity - Multiple Imputation (Subgroup Analysis)
14.2.3.3.5	ITT	Overall Assessment of Erythema Score of 0 at Week 8 by Gender - Multiple Imputation (Subgroup Analysis)
14.2.3.3.6	ITT	Overall Assessment of Erythema Score of 0 at 8 by Ethnicity - Multiple Imputation (Subgroup Analysis)
14.2.3.3.7	ITT	Overall Assessment of Erythema Score of 0 at Week 8 by Race - Multiple Imputation (Subgroup Analysis)
14.2.3.3.8	ITT	Overall Assessment of Erythema Score of 0 at Week 8 by Baseline BSA% - Multiple Imputation (Subgroup Analysis)
14.2.3.3.9	ITT	Overall Assessment of Erythema Score of 0 at Week 8 by Baseline BSA% Tertiles - Multiple Imputation (Subgroup Analysis)
14.2.3.3.10	ITT	Overall Assessment of Erythema Score of 0 at Week 8 by Fitzpatrick Score - Multiple Imputation (Subgroup Analysis)
14.2.3.3.11	ITT	Overall Assessment of Erythema Score of 0 at Week 8 by Body Part Involvement - Multiple Imputation (Subgroup Analysis)
14.2.3.4	ITT	Summary of Overall Assessment of Erythema by Study Visit – Observed Data
14.2.3.5	ITT	Change from Baseline in Overall Assessment of Erythema by Study Visit – Observed Data (ANCOVA)
14.2.4.1	ITT	Overall Assessment of Scaling Severity Grades by Study Visit - Multiple Imputation (Primary Analysis)
14.2.4.1.s	ITT	Overall Assessment of Scaling Severity Grades by Study Visit - Multiple Imputation (Primary Analysis, Supplemental Estimand)
14.2.4.2.1	ITT	Overall Assessment of Scaling Severity Grades by Study Visit – Observed Data (Sensitivity Analysis) Categorical Results

Table Number	Population	Table Title/Summary
14.2.4.2.2	ITT	Overall Assessment of Scaling Score of 0 at Week 8 – Non-responder Imputation (Sensitivity Analysis) Categorical Results
14.2.4.3.1	ITT	Overall Assessment of Scaling Score of 0 at Week 8 by Response to Topical Corticosteroids - Multiple Imputation (Subgroup Analysis)
14.2.4.3.2	ITT	Overall Assessment of Scaling Score of 0 at Week 8 by Response to Topical Antifungals - Multiple Imputation (Subgroup Analysis)
14.2.4.3.3	ITT	Overall Assessment of Scaling Score of 0 at Week 8 by Age Group - Multiple Imputation (Subgroup Analysis)
14.2.4.3.4	ITT	Overall Assessment of Scaling Score of 0 at Week 8 by Age Group - Multiple Imputation (Subgroup Analysis)
14.2.4.3.5	ITT	Overall Assessment of Scaling Score of 0 at Week 8 by Gender - Multiple Imputation (Subgroup Analysis)
14.2.4.3.6	ITT	Overall Assessment of Scaling Score of 0 at Week 8 by Ethnicity- Multiple Imputation (Subgroup Analysis)
14.2.4.3.7	ITT	Overall Assessment of Scaling Score of 0 at Week 8 by Race- Multiple Imputation (Subgroup Analysis)
14.2.4.3.8	ITT	Overall Assessment of Scaling Score of 0 at Week 8 by Baseline BSA% - Multiple Imputation (Subgroup Analysis)
14.2.4.3.9	ITT	Overall Assessment of Scaling Score of 0 at Week 8 by Baseline BSA% Tertiles - Multiple Imputation (Subgroup Analysis)
14.2.4.3.10	ITT	Overall Assessment of Scaling Score of 0 at Week 8 by Fitzpatrick Score - Multiple Imputation (Subgroup Analysis)
14.2.4.3.11	ITT	Overall Assessment of Scaling Score of 0 at Week 8 by Body Part Involvement- Multiple Imputation (Subgroup Analysis)
14.2.4.4	ITT	Summary of Overall Assessment of Scaling by Study Visit - Observed Data
14.2.4.5	ITT	Change from Baseline in Overall Assessment of Scaling by Study Visit – Observed Data (ANCOVA)
14.2.5.1	ITT*	Summary of Scalpdex Total Score by Study Visit - Observed Data
14.2.5.2	ITT*	Change from Baseline in Scalpdex Total Score by Study Visit - Observed Data (ANCOVA)
14.2.5.3	ITT*	Summary of Scalpdex Score - Emotions Scale by Study Visit - Observed Data
14.2.5.4	ITT*	Change from Baseline in Scalpdex Score - Emotions Scale by Study Visit - Observed Data (ANCOVA)
14.2.5.5	ITT*	Summary of Scalpdex Score - Symptoms Scale by Study Visit - Observed Data
14.2.5.6	ITT*	Change from Baseline in Scalpdex Score - Symptoms Scale by Study Visit - Observed Data (ANCOVA)
14.2.5.7	ITT*	Summary of Scalpdex Score - Functioning Scale by Study Visit - Observed Data
14.2.5.8	ITT*	Change from Baseline in Scalpdex Score - Functioning Scale by Study Visit - Observed Data (ANCOVA)

Table Number	Population	Table Title/Summary
14.2.5.9	ITT*	Scalpdex Individual Questionnaire Responses by Study Visit (Categorical)
14.2.5.10	ITT*	Scalpdex Individual Questionnaire Responses by Study Visit (Continuous)
14.2.6.1	ITT	Summary of Dermatology Life Quality Index (DLQI) by Study Visit - Observed Data
14.2.6.2	ITT	Change from Baseline in Dermatology Life Quality Index (DLQI) by Study Visit - Observed Data (ANCOVA)
14.2.6.3	ITT	Summary of Children's Dermatology Life Quality Index (CDLQI) by Study Visit - Observed Data
14.2.6.4	ITT	Change from Baseline in Children's Dermatology Life Quality Index (CDLQI) by Study Visit - Observed Data (ANCOVA)
14.2.7.1	ITT	Summary of Body Surface Area (%) by Study Visit - Observed Data
14.2.7.2	ITT	Change from Baseline in Body Surface Area (%) by Study Visit - Observed Data (ANCOVA)
14.3	Safety Summary	
14.3.1.1	Safety	Overall Summary of Treatment Emergent Adverse Events
14.3.1.2	Safety	Treatment Emergent Adverse Events by System Organ Class and Preferred Term
14.3.1.3	Safety	Treatment Emergent Adverse Events by System Organ Class, Preferred Term, and Maximum Severity
14.3.1.4	Safety	Treatment Emergent Adverse Events by System Organ Class, Preferred Term, and Strongest Relationship to Study Drug
14.3.1.5	Safety	Treatment Emergent Adverse Events of Preferred Term in Descending Order
14.3.1.6	Safety	Treatment Emergent Serious Adverse Events by System Organ Class and Preferred Term
14.3.1.7	Safety	Treatment Emergent Adverse Events Leading to Study Drug Discontinuation by System Organ Class and Preferred Term
14.3.1.8	Safety	Treatment Emergent Adverse Events Leading to Study Discontinuation by System Organ Class and Preferred Term
14.3.2.1	Safety	Quantitative Summary of Investigator Local Tolerability Assessment (Dermal Response) by Study Visit
14.3.2.2	Safety	Categorical Summary of Investigator Local Tolerability Assessment (Dermal Response) by Study Visit Categorical Results
14.3.2.3	Safety	Categorical Summary of Investigator Local Tolerability Assessment (Other Effects) by Study Visit Categorical Results
14.3.2.4	Safety	Quantitative Summary of Subject Local Tolerability Assessment by Study Visit

Table Number	Population	Table Title/Summary
14.3.2.5	Safety	Categorical Summary of Subject Local Tolerability Assessment by Study Visit Categorical Results
14.3.3.1	Safety	Summary of Clinical Chemistry Laboratory Results (Standard Units) by Study Visit
14.3.3.2	Safety	Shift from Baseline in Clinical Chemistry Laboratory Results (Standard Units) by Study Visit
14.3.3.3	Safety	Summary of Hematology Laboratory Results (Standard Units) by Study Visit
14.3.3.4	Safety	Shift from Baseline in Hematology Laboratory Results (Standard Units) by Study Visit
14.3.3.5	Safety	Summary of Quantitative Urinalysis Laboratory Results (Standard Units) by Study Visit
14.3.3.6	Safety	Shift from Baseline in Quantitative Urinalysis Laboratory Results (Standard Units) by Study Visit
14.3.3.7	Safety	Summary of Qualitative Urinalysis Laboratory Results (Standard Units) by Study Visit
14.3.4.1	Safety	Summary of Vital Signs by Study Visit
14.3.4.2	Safety	Change in Weight from Baseline by Study Visit
14.3.4.3	Safety	Shift from Baseline in BMI by Study Visit
14.3.4.4	Safety	Change in Weight from Baseline by Study Visit – by Weight Loss Intentional/Non-Intentional
14.3.4.5	Safety	Shift from Baseline in BMI by Study Visit - by Weight Loss Intentional/Non-Intentional
14.3.5	Safety	Shift from Baseline in Patient Health Questionnaire (PHQ-8)/Modified PHQ-Adolescents by Study Visit
14.3.6	Safety	Summary of CDI-2 by Study Visit
14.3.7	Safety	Summary of Columbia-Suicide Severity Rating Scale (C-SSRS) Suicidal Ideation and Suicidal Behavior by Study Visit
14.3.8	Safety	Summary of Physical Examination by Study Visit
14.3.9	Safety	Summary of Concomitant Medications by Anatomic Therapeutic Chemical (ATC) Class Level 4 and Preferred Term
14.3.10	Safety	Summary of Pigmentation Assessment by Race
14.3.10.1	Safety	Shift from Baseline in Hypopigmentation by Study Visit
14.3.10.2	Safety	Shift from Baseline in Hyperpigmentation by Study Visit
14.4	Pharmacokinetic Data	
14.4.1	PK	Summary of Pharmacokinetic Concentration Results by Study Visit

\*Analyses of Scalpdex will be limited to subjects in the ITT population who have Seborrheic Dermatitis involvement on the scalp

